4.4.2 Secondary Efficacy Variables

See [Section 4.5](#).

4.4.3 Handling of Missing Values/Censoring/Discontinuations

Subjects who withdraw from the study early will be included in the study analysis up to the point of withdrawal. Subjects who withdraw will not be replaced. No data will be imputed in the case of dropouts or missing data.

4.5 Analysis of Secondary Objectives

The mITT population will be considered as primary population for secondary analyses.

4.5.1 Efficacy (Secondary)

The secondary efficacy variables with corresponding comparisons are as follows:

- Change from baseline in Tactile threshold at 4 and 8 weeks; “test product versus negative control” and “positive control versus negative control”.
- Change from baseline in Schiff sensitivity score at 4 weeks; “test product versus negative control” and “positive control versus negative control”.
- Change from baseline in Schiff sensitivity score 8 weeks; “positive control versus negative control”.

Tactile score including the change is derived in the same manner as for the Schiff score, i.e., derived as the average score of the 2 test teeth. The change from baseline is derived from the individual teeth first before calculating the average change of the 2 test teeth. The tooth recorded as >20 g (for screening and baseline) or >80 g (for post baseline) will be rounded up to the next increment of 10g for the calculation of average tactile threshold (g).

Schiff sensitivity score calculated as the average score of the 2 test teeth for secondary efficacy variables will be summarized in [Table 14.2.2.1.1](#). Descriptive statistics (n, missing, mean, SD, SE, median, minimum, and maximum) will be presented for Tactile threshold (g) calculated as the average score of the 2 test teeth at each assessment time point together with the change from baseline in [Table 14.2.3.1.1](#) for all subjects in mITT population by study product. Raw means (\pm SE) of the Tactile threshold (g) at each time point will be plotted by study product in [Figure 14.2.2](#) for all subjects in mITT population.

Change from baseline in Schiff sensitivity score for secondary efficacy variables will be analyzed as per the primary variable ([Table 14.2.2.1.2](#)). Change from baseline in Tactile threshold (g) for secondary efficacy variables will be analyzed using ANCOVA with study product and baseline Schiff stratification as factors and baseline Tactile threshold as a covariate ([Table 14.2.3.1.2](#)).

The assumption of normality and homogeneity of variance in ANCOVA model will be assessed as described for the primary efficacy analysis.

Stannous fluoride (SnF₂)
216954

If there is more than 10% difference in the overall number of subjects between PP and mITT populations, a summary and analysis of the secondary efficacy variable (Tactile threshold) will be presented for the PP population in [Table 14.2.3.2.1](#) and [Table 14.2.3.2.2](#), respectively.

4.5.2 Pharmacokinetic (Secondary)

N/A

4.6 Analysis of Safety

All safety data will be reported for the Safety Population as per actual study product received. The safety profile of the study products will be assessed with respect to AEs, OST findings, OHT findings and exposure.

4.6.1 Adverse Events and Serious Adverse Events

All AEs will be reviewed by the Clinical Research Scientist or Designee prior to database lock and will be coded to a system organ class (SOC) and preferred term (PT) using the Medical Dictionary for Regulatory Activities (MedDRA).

AEs will be classified as oral and non-oral on the AE page of eCRF.

Treatment emergent adverse events (TEAEs) are defined as new AEs that occur on or after the start date of first study product usage (if this date is missing a suitable alternative will be used e.g., date of randomization). AEs with an onset date/time prior to the first study product usage will be considered as non-treatment emergent.

The following summary tables and listings will be presented by study product and overall:

- Table of TEAEs by SOC and PT ([Table 14.3.1.1](#)).
- Table of TEAEs by Oral/Non-Oral and PT ([Table 14.3.1.2](#)).
- Table of treatment-related TEAEs by SOC and PT ([Table 14.3.1.3](#)).
- Table of treatment-related TEAEs by Oral/Non-Oral and PT ([Table 14.3.1.4](#)).
- Table of AEs related to COVID-19 by SOC and PT ([Table 14.3.1.5](#)).
- Listing of all AEs ([Listing 16.2.7.1](#) for all randomized subjects; [Listing 16.2.7.2](#) for non-randomized subjects).
- Listing of all AEs related to COVID-19 Subjects ([Listing 16.2.7.3](#) for all screened subjects)
- Listing of deaths ([Listing 14.3.2.1](#)).
- Listing of non-fatal SAEs ([Listing 14.3.2.2](#)).
- Listing of TEAEs leading to study or product discontinuation ([Listing 14.3.2.3](#)).
- Listing of TEAEs classified as Oral ([Listing 14.3.2.4](#)) [only produced if there are Oral TEAEs].

In the event that there is nothing to report, a null table or listing will be produced.

Stannous fluoride (SnF₂)
216954

In case of more than 5 SAEs reported during the conduct of the study, additional outputs will be prepared to support safety analysis.

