The schedule of activities table provides an overview of the subject visits and study procedures. The investigator may schedule visits (unplanned visits) in addition to those listed on the schedule of activities, to conduct evaluations or assessments required to protect the well-being of the subject.

Procedure/ Assessment	Screening	Study Period		
	Visit 1	Baseline Visit 2 Day 1 (Up to 28 days after Visit 1)	Visit 3 Day 29±3	Visit 4 Day 57±3
Informed consent	X			
Review of Subjects Oral Care Products to Confirm They Don't Contain any Anti-sensitivity Ingredients	X			
Review of Subjects Brushing Habits	X			
Demographics, Ethnicity	X			
Medical History and Prior Medication/Treatment	X			
Concomitant Medications		X	X	X
Full OST Examination	X	X	X	X
Full OHT Examination	X			X
Eligible Teeth Assessments (Dentition Exclusions, EAR, MGI, Tooth Mobility)	X			
Qualifying Tactile Assessment (Yeaple Probe) ¹	X			
Qualifying Evaporative Air Sensitivity (Schiff Sensitivity Score) ¹	X			
Identify Test Teeth	X			
Inclusion/Exclusion Criteria	X			
Subject Eligibility	X			
Dispense Acclimatisation Dentifrice, Toothbrush, Rinsing Cups, Diary and Timer ²	X			
Supervised Brushing with Acclimatisation Dentifrice ³	X			
Subject Adherence and Continuance		X	X	X
Subject completion of DHEQ-15		X		X
Tactile Assessment (Yeaple Probe) ⁴		X	X	X
Evaporative Air Assessment (Schiff Sensitivity Score) ⁵		X	X	X
Confirm Test Teeth ⁶		X		
Stratification and Randomisation		X		
Dispense Randomised Dentifrice, Toothbrush, Rinsing Cups and Diary		X		

ACCLIMATISATION PERIOD 14 TO 28 DAYS

Property of GSK Consumer Healthcare - Confidential

May not be used, divulged, published or otherwise disclosed without the consent of GSKCH

SOP-208661 Clinical Protocol Template v6.0

Supervised Brushing with Allocated Dentifrice and Reminder of Product Usage Instructions ⁷			X	X	
Subjects Bring Study Supplies and Diary to Site			X	X	X
Weight Check of Returned Study Dentifrice and Subject Brushing Video's, and Compliance Discussion ⁷			X	X	X
Adverse Events ⁸	X		X	X	X
Study Conclusion					X

Abbreviations: OST = Oral Soft Tissue; OHT = Oral Hard Tissue; EAR = Erosion, Abrasion, Recession; MGI = Modified Gingival Index; ; SnF₂ = stannous fluoride; DHEQ = Dentine Hypersensitivity Experience Questionnaire.

Footnotes:

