8.2.1.2 Full OST Examination

Full OST examination as described in [Study Assessments](#) will be conducted by the appropriately trained clinical examiner(s) and recorded in the CRF.

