10.1 Definition of an Adverse Event (AE)

An AE is any untoward medical occurrence in a clinical study subject, temporally associated with the use of a study product including any washout or lead-in product (or medical device), whether or not considered related to the study product, including any washout or lead-in product (or medical device).

NOTE: An AE can therefore be any unfavorable and unintended sign (including an abnormal laboratory finding), symptom, or disease (new or exacerbated) temporally associated with the use of a study product including any washout or lead-in product (or medical device).

Events Meeting the AE Definition:

- Any abnormal laboratory test results (hematology, clinical chemistry, or urinalysis) or other safety assessments (e.g. ECG, radiological scans, vital sign measurements), including those that worsen from baseline, considered clinically significant in the medical and scientific judgment of the investigator (i.e., not related to progression of underlying disease).
- Exacerbation of a chronic or intermittent pre-existing condition including either an increase in frequency and/or intensity of the condition.
- New conditions detected or diagnosed after study product administration even though it may have been present before the start of the study.
- Signs, symptoms, or the clinical sequelae of a suspected drug-drug interaction.
- Signs, symptoms, or the clinical sequelae of a suspected overdose of either study product or a concomitant medication. Overdose per se will not be reported as an AE/SAE unless it is an intentional overdose taken with possible suicidal/self-harming intent. Such overdoses should be reported regardless of sequelae.

Property of GSK Consumer Healthcare - Confidential

May not be used, divulged, published or otherwise disclosed without the consent of GSKCH

SOP-208661 Clinical Protocol Template v6.0

- "Lack of efficacy" or "failure of expected pharmacological action" per se will not be reported as an AE. Such instances will be captured in the efficacy assessments. However, the signs, symptoms, and/or clinical sequelae resulting from lack of efficacy will be reported as AE if they fulfill the definition of an AE.

Events NOT meeting the AE definition:

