10.3 Time Period and Frequency for Collecting AE and SAE Information

All AEs, and therefore all SAEs will be collected immediately after a subject provides consent to participate in the study by the completion (signature) of the ICF and until 5 days following last administration of the study product (or last procedure).

Medical occurrences that began before obtaining informed consent will be recorded in the Medical History/Current Medical Conditions section of the CRF not the AE section.

Details recorded by the subject on a diary or similar document that meet the definition of an AE must also be discussed with the subjects and transcribed in the AE section of the CRF.

All SAEs will be recorded and reported to the sponsor or designee immediately and under no circumstance should this exceed 24 hours. The investigator will submit any updated SAE data to the sponsor within 24 hours of it being available.

Investigators are not obligated to actively seek AEs or SAEs after the conclusion of the study participation. However, if the investigator learns of any SAE, including a death, at any time after a subject has been discharged from the study, and he/she considers the event to be reasonably related to the study product or study participation, the investigator must promptly notify the sponsor.

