4.1 Populations for Analysis

4.1.1 Subject Disposition

Screen failures are defined as subjects who consent to participate in the clinical study but are not subsequently randomized. An enrolled subject is a subject who has signed informed consent and is eligible to proceed beyond the screening visit.

Stannous fluoride (SnF₂)
216954

The number of subjects screened, subjects not randomized, and subjects enrolled will be presented for all screened subjects in [Table 14.1.1](#).

[Table 14.1.1](#) will also display the number and percentage of screen failure subjects (subjects not randomized) with reasons why subjects are not randomized. Percentages for screen failure subjects will be based on the total number of subjects screened.

The number and percentage of subjects randomized, who complete the study and who discontinue the study broken down by reason for discontinuation, by study product and overall will also be displayed. The percentages will be based on the total number of subjects randomized.

[Table 14.1.1](#) will also present the number and percentage of subjects in each of the defined analysis populations by study product and overall. Percentages will be based on the number of subjects randomized.

Subject disposition including demographic data (age, sex and race), screening date, study product start date and time, study product end date and time, duration of study product in days (defined as [(last date of study product administration - start date of study product) + 1] for all subjects completing the study as per protocol, and [(date of withdrawal - start date of study product) + 1] for all subjects dropping out of the study), subject status (completer, Yes/No), study completion/withdrawal date, duration in the study in days (defined as [(date of completion or withdrawal - start date of study product) + 1], and the primary reason for withdrawal will be listed ([Listing 16.2.1.1](#)) by study product for all randomized subjects.

Subject disposition information will be listed for non-randomized subjects ([Listing 16.2.1.2](#)), displaying subject number, demographic information (age, sex and race), screening date, reason for screen failure and any further details of reason for screen failure.

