4.3.1 Study Product Compliance and Exposure

Study product compliance data will be summarized for the mITT population and will be assessed by:

- Number of brushings
- Study dentifrice weight

Stannous fluoride (SnF₂)
216954

Number of brushings, brushing compliance (%), number of missed brushings, number of additional brushings and amount of product used (g) will be summarized using descriptive statistics as separate categories by study product in [Table 14.2.1.1](#) by visit and overall.

Number of brushings is defined as: [(date of Visit_n – date of Visit_{n-1} + 1) multiplied by 2 – number of missing brushings + number of additional brushings] by visits, and [(date of Visit 4 – date of Visit 2 + 1) multiplied by 2 – number of missing brushings + number of additional brushings] by overall.

Brushing compliance (%) is defined as: [100 x (Number of brushings / Expected number of brushings)], where expected number of brushings is defined as: [(date of Visit_n - date of Visit_{n-1} + 1) multiplied by 2] by visits, and [(date of Visit 4 – date of Visit 2 + 1) multiplied by 2] by overall.

Study product compliance (number of brushings / brushing compliance [%] / number of missed brushings / number of additional brushings / amount of product used [g]) will be listed in [Listing 16.2.5.1](#) for all randomized subjects by study product.

Supervised study product brushings will also be summarized for the mITT population in [Table 14.2.1.2](#) by visit. In addition, details (including subject number, date and start time of supervised brushing) for supervised study product brushings will be listed ([Listing 16.2.5.2](#)) for all randomized subjects by study product.

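### SAP 4.6.1 has no worsening clause, so a run-in event that worsens on the allocated dentifrice can drop out of the TEAE tables; its date and date/time rules also disagree on Day 1

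*SAP*

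**What the plan says.** SAP 4.6.1 sorts AEs with two sentences. The first defines TEAEs as "new AEs that occur on or after the start date of first study product usage", and if that date is missing it offers a substitute such as the randomisation date. The second says: "AEs with an onset date/time prior to the first study product usage will be considered as non-treatment emergent". Apart from the COVID-19 table, every AE summary table in that section (14.3.1.1 to 14.3.1.4) is restricted to TEAEs. So are the listings of AEs leading to discontinuation (14.3.2.3) and of oral AEs (14.3.2.4).

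Protocol 10.1 defines an AE more widely. It covers aggravated as well as fresh events, extends to any lead-in product, and names as an AE: "Exacerbation of a chronic or intermittent pre-existing condition including either an increase in frequency and/or intensity of the condition".

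On timing, Protocol 10.3 states: "All AEs, and therefore all SAEs will be collected immediately after a subject provides consent". Protocol Table 1-1 places an "ACCLIMATISATION PERIOD 14 TO 28 DAYS" between Screening and Baseline, so collection runs throughout the run-in. Protocol Tables 6-1 and 6-2 show that the run-in dentifrice and the negative control are the same commercial product.

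**The concern.** Safety and oral tolerability form a stated objective, and AEs are the only endpoint listed for it. For a dentifrice, a relevant tolerability signal is oral irritation that was already present and becomes worse on a new paste. The TEAE rule looks only at when an event began, so it can miss that signal.

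The omission need not be even across arms. Subjects allocated to the negative control stay on the paste they used during the run-in. Subjects allocated to the test product or positive control change paste on Day 1. Worsening caused by a change of paste can arise only in those two arms, and it is the kind of event the rule leaves out.

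The second, smaller issue is that the two sentences work at different resolutions, one on dates and the other on date and time. They give different answers for an event on Day 1 before the first brushing.

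**Working it through.** The plan states no figure on this point, so there is none to reproduce. The check applies each sentence, as a rule, to the possible onset patterns. For illustration the first brushing with the allocated dentifrice is put at 10:30 on Day 1; that time is an assumption.

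| Pattern | Sentence 1 (date) | Sentence 2 (date/time) | Result |
|---|---|---|---|
| A. Run-in onset, no worsening | Not a TEAE | Not a TEAE | Consistent |
| B. Run-in onset, worsens on allocated paste, one record | Not a TEAE | Not a TEAE | Worsening not counted |
| C. Day 1 onset at 09:00, before brushing | TEAE | Not a TEAE | Sentences disagree |
| D. Day 1 onset at 11:00, after brushing | TEAE | Not excluded | Consistent |
| E. Onset on Day 10 | TEAE | Not excluded | Consistent |
| F. Worsening entered as a separate AE with onset on Day 10 | TEAE | Not excluded | Counted |

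**Pattern B against F.** Whether worsening is counted depends only on how the site records it.
- Protocol 10.1 would allow a separate entry, because exacerbation is itself an AE.
- Nothing requires one. Protocol 10.6 sends new or updated information about an existing event to the AE page.
- The oral soft tissue (OST) rule in SAP 4.6.2 does not force one either. It is triggered by a change from normal to abnormal relative to Screening. A lesion already abnormal at Visit 2 that later becomes more severe makes no further change of that kind.

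**Pattern C.** The schedule allows it for every subject. Protocol 8.2.1 lists the Visit 2 procedures in order, with the OST examination (8.2.1.2) well before the first supervised brushing (8.2.1.10). An OST change from Screening found at that examination must be recorded as an AE. If the site dates its onset to that visit, sentence 1 includes it and sentence 2 excludes it.

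**Could another section settle it?** Protocol 12.3.4 says only that TEAEs are attributed to the most recent treatment. SAP Table 5-1 does not mention the TEAE definition. Neither gives a worsening rule, an order of precedence between the two sentences, or a convention for a missing onset time.

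**The case against.** The strongest defence is that the two sentences are a general rule followed by a specific exclusion. Read that way, a Day 1 event timed before brushing is simply non-treatment-emergent. The SAP plans to list "study product start date and time" (4.1.1) and the "date and start time of supervised brushing" (4.3.1), so the comparison time is available. This largely stands. A reader might infer a flat contradiction that makes the tables unworkable, but for most timed events the exclusion can govern. What remains is that precedence is not stated and a missing onset time is not covered. Any over-count here should also balance between arms in expectation, because the Visit 2 OST examination is listed before randomisation (8.2.1.8).

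Three other stronger readings do not hold:
- A reader might infer that pain provoked by the probe or air blast on Day 1 would be credited to the allocated paste. Protocol 10.1 excludes expected symptoms of the disorder under study unless they are more severe than expected, so such pain is not ordinarily an AE.
- A reader might infer that worsening is always lost. Pattern F shows that it is counted if entered separately.
- A reader might take the run-in's share of study time, or one subject's weight in an arm, as the size of the problem. Neither measures how often an event starts in the run-in and then worsens.

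It is also fair to say that the data are not lost. Listing 16.2.7.1 shows all AEs for randomised subjects, deaths and non-fatal SAEs are listed without a TEAE restriction, and Table 14.3.4.1 gives OST results by visit and product. That table only separates subjects with abnormalities, without abnormalities, and not examined. A lesion that is present throughout and intensifies therefore looks the same at each visit.

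**Conclusion.** The point holds for worsening. As written, SAP 4.6.1 excludes a run-in event that intensifies on the allocated dentifrice from the TEAE tables and TEAE listings, unless the site happens to enter the worsening as a separate AE. Because the run-in paste is the negative-control product, the omission can selectively hide aggravation after switching in the test and positive-control arms. That is a possibility created by the design; the documents give no evidence that it has happened.

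The Day 1 mismatch is a secondary point of wording. It matters when onset time is missing, or when a Visit 2 finding is dated to the visit and the date rule is programmed.

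The number of events affected cannot be computed, since the documents contain no AE rates. The effect is confined to the safety tables and listings restricted to TEAEs; efficacy is unaffected. The conclusion assumes that some sites' staff will update an existing AE record when an event worsens, as Protocol 10.6 permits.

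**What to change.** Replace the two sentences in SAP 4.6.1 with a single rule and record the change in SAP Table 5-1:

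- A TEAE is an AE with onset date/time at or after the first supervised brushing with the allocated dentifrice, or an AE with earlier onset that increases in intensity, frequency or seriousness after that time.
- A Day 1 AE with missing onset time is treatment-emergent unless it was recorded at a Visit 2 procedure carried out before that brushing.
- Worsening of an existing AE is entered on the AE page as a separate or dated entry.

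The cost is SAP wording, a few lines of derivation, and a minor change to the AE-form completion instructions. The times for product use are already planned. The documents do not show whether AE onset time is collected, so that should be confirmed; where it is absent, the missing-time convention does the work. The worsening clause may add slightly to the number of TEAEs reported. The rule should be settled before unblinding, so that no choice between readings is made with treatment allocation known.

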4.6.2 Other Safety Variables

Other safety variables are listed below:

- COVID-19 infection diagnosis and assessment
- COVID-19 infection diagnosis and assessment – symptoms for symptomatic subjects
- OST examination
- OHT examination
- Exposure

COVID-19 diagnosis and assessment and the symptoms for symptomatic subjects data will be listed ([Listing 16.2.8.1](#) and [Listing 16.2.8.2](#), respectively) for all screened subjects.

An OST examination will be conducted for each subject at every visit prior to any clinical assessments. The examination will be accomplished by direct observation and palpation with retraction aids as appropriate. The examiner will include examination of the labial mucosa (including lips), buccal mucosa, and mucogingival folds, gingival mucosa, hard palate, soft palate, tonsillar area, pharyngeal area, tongue, sublingual area, submandibular area and salivary glands. The results of the examination will be recorded in the CRF as either normal or abnormal with details of any abnormalities. Any observation that changes from “Normal” to “Abnormal” from the screening assessment must be recorded as an AE.

OST will be summarized (number of subjects and percentages with abnormalities, without abnormalities or OST not examined) by visit and study product in [Table 14.3.4.1](#) for all subjects in Safety Population. OST examination will be listed ([Listing 16.2.8.3](#)) for all randomized subjects.

The OHT examination will assess for enamel irregularities, tooth fracture, grossly carious lesions/gross decay, defective/faulty restorations (all direct & indirect restorations including fixed/removal prostheses), non-carious tooth surface loss (abrasion, attrition, abfraction and erosion), any other hard tissue irregularity (e.g. hypo/hypermineralisation, decalcification) and tooth staining. Observations will be listed as “Absent” or “Present” and conditions noted as present will be described. Examination findings will be described and documented in the CRF. Any observation that changes from “Absent” to “Present” from the screening assessment must be recorded as an AE.

Present abnormalities of OHT examination will be listed ([Listing 16.2.8.4](#)) for all randomized subjects.

Exposure to study product is covered under study product compliance and the number of brushings in [Section 4.3.1](#).

Stannous fluoride (SnF₂)
216954

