8.2.2 Visit 3 (Day 29±3) and Visit 4 (Day 57±3)

The following procedures and assessments will take place on Visit 3 (Day 29±3) and Visit 4 (Day 57±3), and where practically feasible they should be completed in the order listed below:

8.2.2.1 Concomitant Medications.

Changes in concomitant medication or non-drug treatments/procedures will be documented in the CRF.

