8.2.2.3 Full OHT Examination

Full OHT examination as described in [Study Assessments](#) will then be conducted by the appropriately trained clinical examiner(s) and recorded in the CRF. **Note: this is only applicable at Visit 4, and should not be completed at Visit 3.**

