3.1 Baseline Definition

For all endpoints, the baseline value will be the latest (non-missing) value obtained prior to any study product administration.

Unless otherwise stated, if baseline data is missing no derivation will be performed and will be set to missing.

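### The soft-tissue AE trigger ignores the pre-dose Visit 2 examination, and silent hard-tissue findings first seen at Visit 4 cannot be placed before or after first product use, so TEAE counts can be misstated

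*SAP*

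**What the plan says.** **Trigger.** Protocol 9.3.1 (OHT), protocol 9.3.2 (OST) and SAP 4.6.2 (both) share one reference visit: a change "from the screening assessment must be recorded as an AE". SAP Table 5-1 rewords the OST categories to Normal and Abnormal to match the eCRF, but keeps Screening as the reference.

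**OST timing.** SAP 4.6.2: "An OST examination will be conducted for each subject at every visit prior to any clinical assessments". Protocol 8.2.1 places the Visit 2 OST examination ahead of the first supervised brushing with the allocated dentifrice, so a pre-dose result exists.

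**OHT timing.** Protocol Table 1-1 marks OHT at Screening and Visit 4. The Visit 2 procedures contain none, and protocol 8.2.2.3 adds: "Note: this is only applicable at Visit 4, and should not be completed at Visit 3".

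**Run-in.** Protocol Table 1-1 puts an "ACCLIMATISATION PERIOD 14 TO 28 DAYS" between Screening and Baseline. Protocol Tables 6-1 and 6-2 show that the run-in dentifrice is the same product as the negative control.

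**Treatment emergence.** SAP 4.6.1 classifies by onset relative to first product use: "AEs with an onset date/time prior to the first study product usage will be considered as non-treatment emergent". It gives no convention for the onset date of a finding known only from an examination.

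**The concern.** Adverse events are the only endpoint listed for the safety objective, and oral TEAEs have their own tables and listing. The examination trigger is the systematic route by which an oral finding becomes an AE record.

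For OST, the trigger looks past the last pre-dose examination to an older one, so a finding that is new relative to the start of treatment can go unrecorded. For OHT, the TEAE tables need to know on which side of first use a finding arose, and no examination is made at that boundary. A silent change during run-in on the acclimatisation dentifrice could be tabulated as treatment-emergent under the test product or the positive control.

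OHT results are otherwise only listed (Listing 16.2.8.4). The TEAE tables are therefore the only planned by-product summary of new hard-tissue findings.

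**Working it through.** The plan states no figure on this point, so there is none to reproduce. The check compares trigger rules for OST and works out time shares for OHT.

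**OST.** Write N for normal and A for abnormal, in the order Screening, Visit 2, Visit 3, Visit 4. The cells show the visits at which each rule's condition is met.

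| Pattern | Against Screening (current) | Visits 3 and 4 against Visit 2 | Against the previous examination |
|---|---|---|---|
| A-N-A-A | none | 3, 4 | 3 |
| A-N-A-N | none | 3 | 3 |
| A-N-N-A | none | 4 | 4 |
| A-A-N-A | none | none | 4 |
| N-A-N-A | 2, 4 | 2 | 2, 4 |
| N-A-A-A | 2, 3, 4 | 2 | 2 |

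In the second rule, Visit 2 is still compared with Screening. Four examinations give 2 × 2 × 2 × 2 = 16 patterns. A fresh on-treatment abnormality (normal at one examination, abnormal at the next, at Visit 3 or 4) needs Visits 2-3-4 to read N-A-A, N-A-N, N-N-A or A-N-A. With either Screening result that makes 4 × 2 = 8 patterns. The four that were abnormal at Screening are the first four rows, and the current rule triggers for none of them.

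Moving the reference to Visit 2 alone recovers three of those four. It still misses A-A-N-A, and it loses the Visit 4 trigger in N-A-N-A. Comparing with the previous examination captures every fresh onset and still triggers at Visit 2 for run-in findings.

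**OHT.** Inputs:
- Run-in r = 14 to 28 days (protocol Table 1-1).
- Second OHT examination at Visit 4, Day 57 ± 3 (protocol 8.2.2), so d = 53 to 59 days after Day 1, nominally 56.

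Run-in share of the interval between the two examinations = r / (r + d):
- Nominal Visit 4: 14/(14 + 56) = 14/70 = 20%, to 28/(28 + 56) = 28/84 = 33%.
- Lowest: 14/(14 + 59) = 14/73 = 19%.
- Highest: 28/(28 + 53) = 28/81 = 35%.

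This is a share of time. It becomes a share of findings only if silent findings arise at a constant rate, which is an assumption and not something the documents state.

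**The case against.** **Screening is a coherent reference for recording.** AEs are collected from consent, and the AE definition in protocol 10.1 covers lead-in products. Treatment emergence is a separate step based on onset. This stands. A run-in OST finding seen at Visit 2 can be dated before first use, so the route from run-in into the TEAE tables is essentially a hard-tissue matter.

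**SAP 3.1.** A reader might infer that the trigger breaches the SAP's own definition, under which "the baseline value will be the latest (non-missing) value obtained prior to any study product administration". The documents do not support that. SAP 3.1 fixes baseline values for endpoints, whereas the trigger is a recording rule. For OHT, Screening is the latest pre-product value anyway.

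**Run-in events can surface earlier.** Subjects keep a diary from Screening, it is reviewed at every visit, and AEs are asked about at Visit 2. A symptomatic event such as a fracture can be reported and dated there. This stands, and limits the OHT point to silent findings.

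**Counting late-detected findings is the protocol's convention.** Protocol 10.1 treats a condition detected after product use as an AE even if it was there before. Causality assessment weighs timing, and treatment-related TEAEs are tabulated separately. This also stands. It is a reason to keep such findings in the count, but it does not make their timing visible.

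**Backstops for OST.** Protocol 10.1 covers exacerbation of an intermittent condition, protocol 10.4 requires directly observed AEs to be reported, and Table 14.3.4.1 and Listing 16.2.8.3 show OST results. These help only in part. Protocol 10.1 also excludes anticipated fluctuations of conditions present at the start that do not worsen, so an investigator could reasonably leave a recurrence unreported. The table gives counts by visit and not within-subject changes, and the listing is not an AE count.

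**Conclusion.** The point holds as a small gap in safety ascertainment.

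- **OST:** an abnormality that clears before treatment and returns on treatment does not meet the examination trigger. How often this happens is not given.
- **OHT:** a silent finding first seen at Visit 4 cannot be placed before or after first use. Run-in is 19% to 35% of the interval between examinations (20% to 33% at nominal Day 57). Such a finding counts as treatment-emergent if it is dated at detection, and SAP 4.6.1 does not say whether it should be.

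Two stronger readings are tempting. One is that the TEAE rate for each product is wrong. The documents give no event counts, an investigator may assign an earlier onset, and late detection counts under protocol 10.1, so the most that can be said is that counts can be misstated. The other is that the comparison between arms is biased. Run-in precedes randomisation, so its findings should be balanced. An equal background leaves the expected difference between arms unchanged and only pulls ratios toward one. No between-arm safety test is planned, and efficacy is not touched.

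**What to change.** 1. **Protocol 9.3.2 and SAP 4.6.2.** Record as an AE any OST observation that is Abnormal and was Normal at the previous examination: Visit 2 against Screening, Visit 3 against Visit 2, Visit 4 against Visit 3. This keeps the run-in trigger and captures recurrences on treatment.
2. **SAP 4.6.1.** Keep counting as TEAEs the findings first detected at the Visit 4 OHT examination with no earlier onset established. Flag them as having onset between Screening and Visit 4, and show TEAE counts by product with and without them.

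The cost is a wording change in each document, one flag in the AE data and one extra table line. The flag requires the detection source of each such AE to be identified, for which the documents describe no field. No additional examination is needed.
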